5.1.4 Subjects will elect not to participate in beet root supplementation study

Subjects to elect not to participate in the beet root supplementation study will be asked to consider participation in an observational study of muscle strength testing that matches the muscle strength testing of those receiving beet root supplementation during their cancer treatment. These subjects will be performing cohort of non-therapeutic interventional subjects who will provide baseline information in a preliminary manner as a comparator to those subjects receiving beet root supplementation. This is not a randomization but rather utilization of subjects who would otherwise not be participating in the clinical trial. These subjects will be compensated for their time in a similar manner to subjects who are on the beet root supplementation study. A separate consent form will be used and a separate registration will be used for these patients.

5.1.5 Testing procedures at Baseline, Midpoint and Endpoint of therapy

All testing procedures, unless otherwise indicated, will be performed at the Markey Cancer Center (MCC) and the Center for Clinical and Translational Science (CCTS). Testing will occur at Baseline (Pre-IMRT), Midpoint (week number 7-8 following IMRT initiation), and Endpoint (4-6 weeks following Midpoint testing). A range of testing times at midpoint and endpoint are provided for subject convenience and flexibility with medical follow-up appointments. Primary outcome measure: 1) IMRT treatment compliance- No delays in treatment of radiation and/or chemotherapy (Cycles: Namely 35 fraction of daily radiation therapy (Monday-Friday) with 100 mg/m² cisplatin on days 1, 21, & 43. Total duration of therapy = 50 days). Treatment compliance will be defined as completion of all radiotherapy or completion of all radiotherapy plus prescribed chemotherapy without dose reduction or delay of radiation therapy that would extend treatment beyond 50 days.; Secondary outcome measures: 1) muscle strength/function, 2) serum/salivary nitrate/nitrite, 3) preservation of fat-free mass (CT/DXA), 4) mucositis symptoms, 5) nutrition assessment, 6) quality of life g. Details of each test are provided in section 9.0.

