5.1.1.1 Dose Specifications

IMRT has been a standard of care in the U.S. beginning in 2005 and is now widely used in practice. Use of H&N IMRT in RTOG protocols (and associated QA) was begun in 2005 in RTOG 0522, as an optional technique. At the close of the accrual phase, approximately 90% of cases enrolled on 0522 (>800 patients) were treated with IMRT. Oropharynx cases comprised 70% of the study population.

IMRT will be delivered in 30-35 fractions over 6-7 weeks, 5 fractions weekly. The primary tumor and involved nodes (CTV1) will typically consist of a 0.5-1.5 cm expansion of the gross tumor volume (GTV) to cover potential local invasion and will be prescribed 2 Gy/fraction, total 55-70 Gy. High-risk sub-clinical disease sites, which include possible local subclinical infiltration at the primary site (primary site CTV2) and first echelon nodes, which are not clinically or radiographically involved (nodal CTV2), should be expanded by 3-5 mm to create PTV2. PTV2 should receive 1.6 Gy/fraction to a total dose of 52.8 Gy to 56 Gy. Lower-risk targets (PTV3) (such as neck nodal levels which are not first echelon nodes and are not adjacent to levels containing grossly involved nodes) will be prescribed 50-52.5 Gy. If the low neck is treated, the preferred technique is to treat with isocentric matching AP or AP-PA fields with larynx block, matched to the IMRT portals just above the arytenoids. The dose will be 2 Gy per fraction prescribed to 3 cm depth to a total dose of 50 Gy in 25 daily fractions. Whole-neck IMRT is allowed. This can be achieved by either boosting the low neck field with an additional 16 Gy in 8 fractions, by an AP or AP-PA fields, or by planning the whole neck using IMRT. In cases of gross involvement of the vallecula or low neck, whole-neck IMRT should be considered. Whole-neck IMRT may also be considered if level VI is considered to be at risk due to gross involvement of level IV nodes. All plans must be normalized such that 95% of the volume of the PTV is covered with prescription dose..

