5.1.1.2 Compliance Criteria

Treatment breaks must be clearly indicated in the treatment record along with the reason(s) for the

treatment break(s). Treatment breaks, if necessary, ideally should not exceed 5 treatment days at a time and 10 treatment days total. Treatment breaks should be allowed only for resolution of severe acute toxicity and/or for intercurrent illness and not for social or logistical reasons. Any treatment break(s) exceeding 2 treatment days for reasons other than toxicity/illness will be considered a protocol deviation. The following define compliance:

- Overall RT treatment time:
 - ≤ 52 days (compliant)
 - > 52 days (non-compliant)
- Up to 57 days for non-medical reasons (such as holiday, machine breakdown) as determined by the treating radiotherapy physician.

Missed treatments due to holidays or logistic reasons can be compensated for by delivering an additional BID treatment during the week, OR treating on the Saturday or Sunday of that week, OR adding to the end of treatment. These additions will not be considered non-compliance.

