- CRNs serving as study personnel may offer observation or administration assistance if patient requests this and may document supplement compliance.
- Patients will be instructed to make up any missed doses by taking up to 1 additional dose per day on the weekend days. Patients will receive 5 doses per week (for M-F) and will be instructed to never exceed 1 dose per day.

4-6 weeks post-IMRT (discharge period):

- After completion of IMRT the participant will be instructed to continue daily (M-F) self-administration (PO or PEG) until completion of endpoint measures.
- For patients requiring supplement administration assistance at discharge, a family member or caregiver will be identified and taught to provide assistance.
- On the day of discharge and during scheduled follow-up visits, the CRA will distribute the pre-measured supplement packets needed for daily administration.
- Participants will continue to follow the supplement mixing protocol and be reminded to consume their assigned supplement within 30-minutes of mixing.
- Supplement compliance will continue to be encouraged by weekly phone calls by study personnel and compliance logs/supplement counts will occur at least twice per month.

Supplementation on Testing Days

On testing days, The BEETELITE™ solution (beet root) will be administered on-campus 20-45 minutes before subjects undergo the baseline, midpoint (following IMRT), and endpoint (4-6 weeks following midpoint) strength/endurance measures. Prior to testing, subjects will not have to refrain from standard oral care, using antibacterial mouth wash, or chewing gum 48 hours before testing sessions because the BEETELITE™ product does not rely on salivation/oral bacteria to convert dietary nitrate to nitrite (23). Previous studies have administered up to 500mL of beet root per day with nitrate concentrations of 5.5 mMol (24), 6.2mMol (7, 25), 5.2mMol (26), and 5.1mMol (27). Plasma nitrite (NO_2^-) levels in these aforementioned studies also increased following dietary nitrate supplementation.

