9.1 Assessment of Body Composition and Quality of Life

9.1.1 Computed Tomography (CT)

Immediately following or preceding radiation simulation (Correlative Day 1) radiation treatment (Correlative Day 2) and follow-up period (Correlative Day 3) at the Markey Cancer Center, subjects will be transported to the ground level of Markey by MCC staff for CT measures.

Computed tomography (CT) images (GE large bore 16 slice) will be used to quantify skeletal muscle and fat area of the right and left thighs, and the right and left forearms of each subject using 100mA with a scanning time of 3 s and a 512 X 512 matrix. With the subject supine, one 10 mm thick cross-section scan of both legs will be taken corresponding to the midpoint between the inguinal crease and the proximal border of the patella, and one 10 mm thick cross-section scan will be taken corresponding to 2/3 the distance from the styloid process of the radius to the olecranon. Tissue area quantification will be determined using corresponding attenuation values of ≥ 200 HU; -190 to -30 HU; and 0-100 HU for bone, adipose tissue, and skeletal muscle, respectively using available software (NIH ImageJ; <http://rsbweb.nih.gov/ij/>). Total thigh fat will be further subdivided into two compartments including the fat above the fascia lata (subcutaneous thigh fat) and below the fascia lata (deep thigh fat). In addition, the skeletal muscle will be subdivided into areas of low attenuation (0-34 HU) representing "fat-rich" muscle, and high attenuation values (35-100 HU) representing muscle with normal fat content. While the forearm scan methodology is unique and has been developed specifically for this study, the method of analyzing thigh composition has been previously described (9). All CT scans will be assessed under the direction of [name].

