10.2 Calendar for Beetroot Supplementation Cohort

Timepoints	Baseline	Weekly during Concurrent Radiation and Cisplatin	Midpoint (After IMRT)	Endpoint (4-6 weeks following Midpoint testing)	Off-treatment	Off study
Studies:						
H&P ¹ VS	X	X	X	X	X	X
TOX	X	X	X	X		
Pregnancy Testing	X					
Muscle Strength and Endurance Testing	X		X	X		
Body Composition (DXA)	X		X	X		
Plasma/Salivary Nitrate/Nitrite	X		X	X		
QOL and Mucositis	X		X	X		
Diet	X		X			
Ct SCAN (body comp)	X		X	X		
Routine Cancer Imaging ²	X			X		X
Treatments:						
Beet Root (daily) ³	X	X	X	X		

1) Abbreviations: H&P=History and Physical examination; PS=ECOG performance status; VS=vital signs (blood pressure, temperature, pulse and respiratory rates, weight and height); TOX=toxicity assessment

2) Routine cancer imaging will be standard of care CT or MRI scans to document disease and response to therapy. These will be required pre-treatment, post-chemoradiation and at 1- and 2-year follow-up (+/- 6 weeks), as per standard of care.

3)Beet root will be self-administered each day (M-F in afternoon)

4)Toxicity will be followed for all patients until (endpoint) testing. Any beetroot related toxicity $>$ grade 2 will be followed until resolution to grade 1 or less.

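### The midpoint visit has two anchors, week 7-8 from the start of IMRT and after IMRT; they leave time since the last fraction uncontrolled and cannot both be met in a long course

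*Combined protocol and SAP*

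**What the plan says.** Section 5.1.5 schedules the tests: "Testing will occur at Baseline (Pre-IMRT), Midpoint (week number 7-8 following IMRT initiation), and Endpoint (4-6 weeks following Midpoint testing". It explains the ranges by patient convenience and fit with follow-up appointments.

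Other places use a different anchor. Section 5.1.3 (supplementation on testing days) has "midpoint (following IMRT), and endpoint (4-6 weeks following midpoint". The calendars for the beetroot cohort (10.2) and the observational cohort (10.3) both label the column "Midpoint (After IMRT". Section 9.1.1 links the second body-composition CT to "radiation treatment (Correlative Day 2", which does not settle whether treatment has ended.

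Course length is not constant. Section 5.1.1.1 states: "IMRT will be delivered in 30-35 fractions over 6-7 weeks, 5 fractions weekly". Section 5.1.1.2 says that breaks "ideally should not exceed 5 treatment days at a time and 10 treatment days total". It treats more than 52 days overall as non-compliant, with up to 57 days for non-medical reasons.

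The endpoint is counted from the midpoint in 5.1.5, yet 5.1.3 describes the final supplementation period as 4-6 weeks after treatment, running until the endpoint measures are done.

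The documents give no window in days from the last fraction, and no rule for short, prolonged or stopped courses.

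**The concern.** Change in strength and body composition is a secondary objective (1.2). Section 13.3 compares cohorts across the nominal time points by repeated measures ANOVA, with no term for when the test took place relative to radiotherapy. Sections 2.2 and 2.5 attribute loss of muscle to treatment, so the interval from the last fraction plausibly matters to what is measured.

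If the midpoint is booked by weeks from the start, that interval depends on the number of fractions and on delay. Fraction number is not balanced between the cohorts, which are not randomized. Delay is part of the primary outcome. If instead the visit is booked after IMRT, there is no stated upper limit. Staff following different sections could test similar patients at different stages of treatment, and the resulting summaries are meant to inform the effect sizes for a larger study.

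**Working it through.** **Inputs.** 30-35 fractions, 5 per week (5.1.1.1); up to 10 missed treatment days as guidance (5.1.1.2); midpoint in week 7-8 from IMRT start (5.1.5); midpoint after IMRT (5.1.3, 10.2, 10.3); endpoint 4-6 weeks, or 28-42 days, after midpoint (5.1.5). Assumptions: day 1 is the first fraction, a Monday; missed sessions are added at the end; after IMRT means the day after the last fraction at the earliest.

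**The plan's own figures.** 30/5 = 6 weeks and 35/5 = 7 weeks, as 5.1.1.1 states. The 50-day duration that 5.1.5 gives for 35 fractions is reached with one missed day; unbroken, the course ends on day 47 (day 49 for other start weekdays).

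**Last-fraction day.** For n sessions (fractions plus missed days, n a multiple of 5), the last day is 7 × n/5 − 2: 30 gives 42 − 2 = 40; 35 gives 49 − 2 = 47; 40 gives 56 − 2 = 54; 45 gives 63 − 2 = 61.

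**Midpoint relative to the last fraction.** Subtract the last-fraction day from each end of the window. Week 7-8 can be read as week numbers (days 43-56) or elapsed weeks (about days 50-57).

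| Course | Last day | Days 43-56 | Days 43-56 that are also after IMRT | Days 50-57 |
|---|---|---|---|---|
| 30 fractions, unbroken | 40 | +3 to +16 | 43-56 | +10 to +17 |
| 35 fractions, unbroken | 47 | −4 to +9 | 48-56 | +3 to +10 |
| 35 fractions, 5 missed | 54 | −11 to +2 | 55-56 | −4 to +3 |
| 35 fractions, 10 missed | 61 | −18 to −5 | none | −11 to −4 |

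**Where the rules collide.** A day that is both after IMRT and no later than day 56 exists only if the course ends by day 55. With a Monday start and 35 fractions, five missed days still fit (day 54); six give 41 sessions and an end on day 8 × 7 + 1 = 57, which does not. With any other start weekday, five missed days already end on day 56. On the days 50-57 reading, the collision starts with a course ending on day 57.

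**Endpoint.** Counting 28-42 days from days 43-56 gives days 71-98. Relative to the last fraction this is 71 − 40 = 31 to 98 − 40 = 58 days for 30 unbroken fractions, 24 to 51 for 35 unbroken, and 10 to 37 for the day-61 course. The post-treatment description in 5.1.3 implies 28 to 42 days. Requiring the midpoint to follow IMRT leaves the 30-fraction range of 31 to 58 unchanged.

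**The case against.** The strongest reply is that week 7-8 is shorthand for the end of treatment. Section 5.1.3 calls IMRT a 7-8 week period, and for the 35-fraction, 50-day course in 5.1.5 the wording works. If the after-IMRT wording governs, nobody is tested during radiotherapy and every negative offset disappears. If the window means elapsed weeks, every unbroken course is finished before the visit. This stands as an account of probable intent, but 5.1.5 does not say it, and the plan still lacks an upper limit and a rule for long courses. The CT wording in 9.1.1 is loose logistics and weak evidence of a third anchor.

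Four stronger readings are tempting and are not supported:

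- A reader might infer that the visit is simply fixed to week 7-8, so that delayed patients are tested mid-treatment. That follows only if 5.1.5 is read alone.
- A reader might quote a 34-day spread (−18 to +16). It sets the latest test in the shortest course against the earliest in an extreme course, again under 5.1.5 alone. Day 61 needs 10 missed days all added at the end, beyond both the 52-day limit and the 57-day allowance; holiday or logistic misses can be made up by twice-daily or weekend sessions. It is not a firm maximum either, since the break limit is guidance and other start weekdays give day 63.
- A reader might infer that fewer delays under beetroot would make those patients look stronger without any muscle effect. The documents give no time course of strength or lean mass after radiotherapy, so neither direction nor size can be claimed.
- A reader might extend the point to mucositis generally. Sections 1.2, 5.1.6 and 9.5 provide weekly grading, so the beetroot cohort's trend does not rest on the midpoint. The point remains only for the observational cohort, whose calendar shows no weekly grading and which 11.1 does not follow for toxicity.

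It is also fair that the affected measures are secondary and exploratory, and that 13.2 disclaims power to compare beetroot with standard of care.

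**Conclusion.** The conflict between 5.1.5 and sections 5.1.3, 10.2 and 10.3 is real and should be resolved, although no primary conclusion depends on it. The two rules sit together comfortably only for a course with little or no delay. Even without breaks, and on the days 43-56 reading, the permitted visit ranges from 3-16 days after the last fraction (30 fractions) to 4 days before through 9 days after it (35 fractions). For courses ending on day 56 or later, both rules cannot be followed. On the days 50-57 reading, the extreme day-61 course would still be tested 4-11 days before its last fraction. The endpoint is inconsistent in the same way.

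The comparisons at risk are strength, DXA, CT and quality of life, plus mucositis in the observational cohort only. The compliance endpoint does not use this visit. The figures assume a Monday start and missed sessions added at the end. How many courses will pass day 55 is unknown: section 2.1 says that about half of chemoradiation trial subjects finish radiation within 50 days, but gives no distribution beyond that.

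**What to change.** In 5.1.5, define the midpoint as a stated window of days after the last radiation fraction delivered, or after radiotherapy is stopped early, in both cohorts. Count the endpoint 4-6 weeks from that same date, not from the midpoint test. Use the same wording in 5.1.3, 9.1.1, 10.2 and 10.3; because 5.1.3 ties the supplementation period to the endpoint visit, those passages must be reconciled together. The sponsor should choose the window width; a range of days keeps the scheduling flexibility that 5.1.5 asks for.

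Record days since last fraction at each test and report them by cohort with the results in 13.3.

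The cost is amendment wording and one derived variable, with no added visits. The small downside is that visits for delayed patients can be booked only once the finish date is known.

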5.1.6 General Testing Procedures and Blinding

A trained CCTS exercise physiologist will complete DXA, Bidex strength/endurance measures, and handgrip dynamometry under the direction of Drs. [name] and [name]. CT measures will be performed by trained MCC staff at baseline, midpoint and endpoint, and will be overseen by [name]. Quality of life (FACT H/N version 4) assessment will be administered by the study exercise physiologist. Assessment for toxicity to radiotherapy or chemoradiotherapy and mucositis assessment will be completed on a weekly basis by [name] and will serve as a safety measure. Nutrition intake will be collected during clinical status checks by a trained clinical nutrition graduate student under the direction of [name].

5.2 General Concomitant Medication and Supportive Care Guidelines

Patients will undergo clinical toxicity assessment on a weekly basis in the clinic. Toxicity assessment will be made as per the CTCAE version 4.0 as assessed by medical and radiation oncology physicians. All toxicities and their attribution will be recorded, regardless of attribution. Of particular interest will be toxicities that are possible, probable or definitely related to administration of beet root, as determined by the treating physician or related to acute radiation toxicities of: mucositis, radiation skin reaction, radiation pneumonitis, or dry mouth. Staging of tumors will be done as per the multidisciplinary head/neck team using AJCC staging manual version 7. The response to treatment will be made by repeating clinical and radiological studies as per standard of care (6- 12 weeks) and repeated during follow up as per NCCN guidelines. Patients will be followed until resolution of all grade 2 or greater toxicities.

Supportive Care:

Mucositis:

If patients require supporting care for mucositis-related pain during concurrent chemotherapy and radiation treatment, the following regimen is recommended, but the local standard of care is permitted.

- A compound containing viscous lidocaine and magnesium aluminum oxide (Maalox®) or sucralfate;
- Liquid or solid oxycodone, 5-10 mg, every 3-4 hours as needed.

Nutritional Support:

Patients may take nutritional supplements (i.e. protein/kcal), such as Ensure®, but should refrain from other nutritional supplements (i.e. nutraceuticals). Patients may take appetite stimulants as prescribed by treating physicians. Feeding tubes are encouraged to prevent malnutrition.

Febrile neutropenia will be managed according to accepted guidelines. Measures may include appropriate laboratory testing, including blood and urine cultures. If a source for the fever is not identified or the fever resolves when the neutrophil count recovers, antibiotics may be discontinued and the patient observed.

Antiemetics: Antiemetics may be necessary. The use of antiemetics is encouraged to prevent dehydration. The specific drugs will be left to the treating physician's discretion.

Other Concomitant Medications: Therapies considered necessary for the wellbeing of the patient might be given at the discretion of the investigator. Other concomitant medications should be avoided except for analgesics, chronic treatments for concomitant medical conditions, or agents required for life-threatening medical problems. All concomitant medications, including over-the-counter and/or alternative medications, must be recorded.

Other Anticancer or Experimental Therapies: No other anticancer therapy (including chemotherapy, radiation, hormonal treatment or immunotherapy) of any kind is permitted during the study period. No other drug under investigation may be used concomitantly with the study drug.

Treatment For Diarrhea: Diarrhea should be treated promptly with appropriate supportive care, including loperamide. Instruct patients to begin taking loperamide at the first signs of: 1) poorly formed or loose stool, 2) occurrence of more bowel movements than usual in one day, or 3) unusually high volume of stool. Loperamide should be prescribed in the following manner: 4 mg at first onset of diarrhea, then 2 mg after each unformed stool. Daily dose should not exceed 16 mg/day. Loperamide should not be taken prophylactically. Advise patients to drink plenty of clear fluids to help prevent dehydration caused by diarrhea. Avoid loperamide if there is blood or mucus in the stool or if diarrhea is accompanied by fever. If grade 3 or 4 diarrhea develops, discontinue further treatment until the diarrhea has recovered to grade 1 or less. Although unlikely, in the event that fatigue is encountered, medications such as modafinil and methylphenidate may be used at the investigator's discretion.

